12. STUDY TIMELINES

Subject participation is limited to the workshop session, post-workshop cervical cancer screening and surveys, and follow up call from CHWs on results of screening tests (if indicated).

- Duration of participation involvement is estimated to be between two to three hours.
- Activities involved is primarily attendance at a 45-minute workshop followed by post-workshop survey (estimate to complete in three- to five-minutes)
- Participants who opt for screening for cervical cancer after workshop completion will spend an additional 30 to 60 minutes waiting for sample collection. Actual time for sample collection will be between five- to ten- minutes.
- Participants will be contacted by phone regarding their results on screening tests by MCHH CHWs. Those with positive results will be asked to return to the community center to discuss the results in-person with CHWs, with a clinician available by virtual methods.

Anticipated duration to enroll all study participants will be over 16 months. Estimated date for researchers to complete this study (including primary analysis) is over 24 months starting from IRB approval.

A research subject will be defined as “enrolled” in the study when they meet the following criteria:

- The subject has been consented by study staff.
- The PI has verified that the subject meets all of the inclusion criteria.
- The PI has verified that subject meets none of the exclusion criteria.
- The subject has been assigned to the protocol by study staff.

The project period is estimated to be two years from date of IRB approval. Table 2 summarizes the activities and evaluations that will take place during the project, over a 24-month time period, and which subject participants are involved with them.

Table 2. Study Calendar

Month	1	2	3	4	5	6	7	8	9	10	11	12	13	14	15	16	17	18	19	20	21	22	23	24
Activities																								
Develop Recruitment Strategy	X	X																						
Recruitment			X	X	X	X	X	X	X	X	X	X	X	X	X	X	X	X	X	X				
Monthly Workshops					X	X	X	X	X	X	X	X	X	X	X	X	X	X	X	X	X			
Follow-up on Screening Results					X	X	X	X	X	X	X	X	X	X	X	X	X	X	X	X	X	X	X	
Evaluation																								
Participation Rates					X	X	X	X	X	X	X	X	X	X	X	X	X	X	X	X				
Post Workshop Surveys					X	X	X	X	X	X	X	X	X	X	X	X	X	X	X	X	X	X		

13. PROCEDURES INVOLVED

13.1 Project Activities

13.1.1 Pre-Participation Intake

Intake will be done upon recruitment, after informed consent is obtained and prior to start the assigned workshop. Forms to be used are the standard intake forms used by MCHH for previous workshop participations and gathers information such as demographics, primary care physician (PCP), and insurance coverage (full intake form in Appendix A). Intake forms are assigned an ID # which will be used to extract data for this research program. [name] (MCHH Director) will maintain original intake forms at the MCHH community center and participant identities to the study ID separately from other data. Following information from the intake form will be collected for this research program:

- ID Number
- First and last initials
- Workshop Date
- Ethnicity
- Date of Birth
- Gender
- Month and year of previous Pap Test
- Type of Insurance
- Answer to the following question “What reasons may be stopping you from getting a Pap Test?” (options below)

 No symptoms	 I don't want to know the results
 No transportation	 Childcare
 Too expensive/No insurance	 No family history of cervical cancer
 I don't know where to go	 My doctor never mentioned it
 Spouse will not allow it	 Embarrassed
 I'm too busy/No time	 Long wait to get an appointment
 I am afraid it will hurt	 None

If a participant has a PCP, MCHH can fax or mail the results of their screening tests directly to their PCP. For participants who do not have a PCP and would like to establish with one, a list of available providers in the area accepting new patients will be obtained prior to the start of the research study.

Providers accepting new patients will be oriented by phone by a research team member prior to the start of the study. They will be provided with a brief overview of the research study and purpose. In addition, when receiving participant results on cervical cancer screening, cover letter will include a brief overview of the research project, purpose, recommend follow-up, and need for patient to establish as a new patient to their clinic.

13.1.2 Workshops

All workshop materials were previously developed through a partnership with [name] and MCHH, with support through a community advisory panel. Workshops consist of translated materials into Hmong, Burmese, Karen and Karen, with methods that include flip charts, video, and hands-on models to provide education on cervical cancer screening and prevention. Materials were developed to target mother-daughter pairs although for this research will target only women age 25 to 65 which is the target for HPV only screening (versus co-testing HPV and pap smear). Participants self-select which workshop day they would like to participate in

although are blinded which group the workshop belongs to. Workshops are differentiated based on belonging to the control or intervention group.

- **Control** workshops are workshops where participants are provided education on standard-of-care for cervical cancer screening such as pap smear and HPV testing through clinician-collection methods using speculum and cervical swabs.
- **Intervention** workshops are workshops where participants are provided all the same education as control as well as additional education on self-collection for HPV only testing using vaginal swab as an additional method.

13.1.3 Post-Workshop Survey Collection

All participants after education session, regardless of participation in post-workshop screening for cervical cancer, will answer questions on two separate surveys. The MCHH post-workshop evaluation survey (MCHH-PES) has been used previously after workshops that were hosted by MCHH. The UW Health Post-Workshop Satisfaction Survey (UW-PSS) will be an additional survey done to cover remaining questions on participant satisfaction.

13.1.3.1 MCHH Post-Workshop Evaluation Survey (MCHH-PES)

Data collected on the original intake form by MCHH includes the following questions (Figure 3) and will be collected in this study in the same format. Survey will be administered verbally by CHWs in the participants native language. Paper copies of the survey will remain with MCHH and responses copied into Qualtrics survey and continued with questions in the next section (13.2.2. UW Health Researchers Post-Workshop Satisfaction Survey).

Figure 3. MCHH-PES Questions

Participant Evaluation

After today's workshop, how likely are you to...?	Not likely	Neutral	Very Likely	
1. Receive a Pap/Pelvic exam this year or as recommended?	1	2	3	4
2. Spread the word about the screenings available to your family members?	1	2	3	4
3. To encourage your family members to get screened?	1	2	3	4
4. Practice healthy behaviours that can reduce your risks for cervical cancer?	1	2	3	4

13.1.3.2 UW Health Post-Workshop Satisfaction Survey (UW-PSS)

Additional survey questions will be administered verbally by CHWs and answers recorded in Qualtrics for data collection. Responses will not be linked to the study ID or other identifiable information. Theme of survey questions is below (full survey in Appendix C):

- Comfort with method (either self-collection or clinician-collection)
- How likely would the participant get screening for cervical cancer again?
- If self-collection (or clinician-collection) was an option, would they have preferred this method.

- If not getting screening today, will they go for screening in the near future?
 - o If not why? Where?
- Understanding of instructions (self-collection)

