11. STUDY INTERVENTION

This randomized controlled trial will be done in partnership with MCHH. Previous partnership with MCHH and UW-Madison researchers developed cervical cancer educational workshops designed by CHWs to provide innovative mixed-modality education consisting of pictographs, flipcharts, videos, and hands-on models. These workshops to be conducted in Hmong, Karen, and Burmese and Karen languages were tested in mock workshops with Hmong and Karen participants and through a community advisory panel prior to dissemination. This approach caters to the unique culture and communication styles of Southeast Asian immigrant and refugee populations.

All workshops will be conducted by the CHWs on the study team. If the CHW is not fluent in the target language (such as Karen or Burmese), then the CHW will conduct all study activities in English with a translator available to translate all activities.

All participants attending a workshop will be randomized as a group to either a control or intervention group. Workshops in the control group will provide education recommending standard of care (clinician-collected hrHPV testing and cytology screening). Workshops in the intervention group will be offered the same education with additional education on the option of self-collection (HPV testing only) for their screening method. All participants will have the same basic demographic information collected in MCHH's standard intake form with an additional question on current barriers to screening.

Participants will self-select which workshop day they would like to attend depending on their preferred language. Participants can attend any available date a workshop is being offered until filled. Participants will be blinded to knowing which workshops are control or intervention groups. Participants during consent will be made aware there are two different groups and the difference between the intervention and control group is the education provided and screening method offered at the end of the education session. Participants will be provided the full study details at the end of their participation.

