We anticipate a total of thirty workshops, fifteen of which will be control and fifteen of which will be intervention, will be planned in total over a sixteen-month period (Table 1). All workshops will have 8 participants recruited due to limited space of the community center, time, and to accommodate physical spacing needs. There will be two workshop sessions per day (one in the morning and one in the afternoon).

Table 1. Planned Number of Hmong and Karen Participants in the Intervention and Control Workshops

Intervention Workshop	1	2	3	4	5	Total
Hmong	8	8	8	8	8	40
Karen	8	8	8	8		36
Karen	8	8	8			24
Burmese	8	8	8			24
Control Workshop						
Hmong	8	8	8	8	8	40
Karen	8	8	8	8		36
Karen	8	8	8			24
Burmese	8	8	8			24

[figure not shown]
After workshop conclusion, participants will be offered same-day on-site cervical cancer screening depending on assignment in the control or intervention group (clinician-collected screening or self-collection screening, respectively). Participants, regardless of engagement in screening, will then complete a post-evaluation workshop survey (consisting of two surveys, see Appendix C).

Due to ethical concerns and our hypothesis that this population is less likely to do cervical cancer screening if offered clinician-collected screening only. Participants in the control workshops who answer “yes” on the survey to the question “If given the option, instead of having a clinician collect the sample, would you want to collect the sample on your own?,” will be subsequently offered self-collection for their screening method. CHWs will provide to these participants a 5-minute 1-on-1 instruction tutorial on self-collection, translated handout, private room to collect a sample, and then samples sent to the laboratory per protocol.

Similarly, participants will be made aware during the education of the self-collection method, that this is not a usual method that is offered in many clinical practices. If a participant were to visit their usual primary care doctor for an exam, a pelvic examination to obtain a clinician-collected cervical swab for HPV testing and pap smear is the usual method which they should anticipate. We are offering self-collection as studies show growing validity of HPV self-sampling, particularly among hard-to-reach populations.¹⁴⁻¹⁸ With this understanding, self-collection will be offered and encouraged although if participants desire clinician-collection instead this is option will also be made available.

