16.2 Data Storage and Maintenance

Data will be stored in compliance with HIPAA regulations on encrypted UW research servers in the Department of Family Medicine and Community Health. All records including study enrollment information will be housed in compliance with regulations indefinitely until the analysis is complete. The process of destroying of these records post-analysis will comply with applicable UW or policies for research records.

The study ID, date of workshop attendance, age, zipcode, type of screening done, and screening results will be stored in REDCap Institute for Clinical and Translational Research (ICTR). Portable devices will be used to access secure web-based application of ICTR's RedCap. No data will be stored locally on the device. Only encrypted devices will be used.

Research Electronic Data Capture (REDCap) is a largely self-service, secure, web-based application for building and managing data collection forms. REDCap provides data management functionality by allowing the development of instrument and surveys to support data capture for research studies.

Post-workshop survey results will be stored in Qualtrics and not linked to study ID, results will be entirely anonymous. Paper copies of the intake form will be stored in a locked location at the Milwaukee Consortium for Hmong Health.

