20.3.2 Secondary Outcome Measures and Analysis

Qualitative survey data will be obtained through pre- and post-workshop surveys to evaluate the impact of the educational workshops.

Further statistical support for this program will be obtained through consultation with statisticians in the UW-Madison SMPH and/or UW Carbone Cancer Center Biostatistics Shared Resource. For quantitative data, differences will be tested with Wilcoxon Rank-Sum tests for continuous or ordinal categorical data, Chi-Squared tests for unordered categorical data, and binomial tests for dichotomous data.

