APPENDIX C: UW Health Researchers Post-Workshop Satisfaction Survey (UW-PSS)

Due to the number of skip logics, the survey is best viewed through Qualtrics

Link: https://uwmadison.co1.qualtrics.com/jfe/form/SV_bQT22KcJ9g7Qklw

Community Health Outreach to Increase Cervical Cancer Education and Self-Collection Screening (CHOICES) Program among Burmese and Hmong Women in Wisconsin.

This post-workshop participant survey is designed to be filled out with the guidance of Community Health Workers.

Please do not have the participant fill this information on their own.

Please copy the below information from the paper MCHH intake form:

Section A

After today's workshop, how likely are you to....?

	Not Likely	Somewhat unlikely	Neutral	Somewhat likely	Very Likely
1) Receive a Pap/Pelvic exam this year or as recommended?					
2) Spread the word about the screenings available to your family members?					
3) To encourage your family members to get screened?					
4) Practice healthy behaviors that can reduce your risks of cervical cancer?					

What workshop did the participant attend?

Clinician-collection education → Continues to Section B

Self-collection education → Skip to Section D

Section B

Did the participant get screening for cervical cancer today? (Clinician Collected)

Yes

No → Skip to Section C

Section B (continued)

How comfortable did you feel with this method?

- Extremely comfortable
- Somewhat comfortable
- Neither comfortable nor uncomfortable
- Somewhat uncomfortable
- Extremely uncomfortable

How likely would you get screening for cervical cancer again?

- Extremely likely
- Somewhat likely
- Neither likely nor unlikely
- Somewhat unlikely
- Extremely unlikely

In the workshop you attended today, we did not discuss self-collection as an option.

If self-collection was an option, would you have preferred this method?

- Yes
- Maybe
- No

Any remaining questions you have about the workshops or about cervical cancer?

Survey End

Section C

Will you get screening for cervical cancer in the near future (within the next year)?

- Yes
- Maybe
- No

Do you have any concerns with getting screening for cervical cancer?

[figure not shown]
Where would you go to get cervical cancer screening?

- My usual doctor or other clinician
- The health department
- Will return to the community center
- Another health care provider (not yet found)
- Not sure yet

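### The UW-PSS survey as printed records the arm but not the workshop, so any between-arm comparison of its own items could not be analysed by the unit that was randomised

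*Combined protocol and SAP*

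**What the plan says.** **Randomisation.** Section 11 makes the workshop the unit: "All participants attending a workshop will be randomized as a group to either a control or intervention group". It plans the numbers as follows: "We anticipate a total of thirty workshops, fifteen of which will be control and fifteen of which will be intervention", and "All workshops will have 8 participants recruited due to limited space of the community center". It adds that "There will be two workshop sessions per day", so a date alone does not identify a workshop.

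**Survey record.** Section 13.1.3.2 states: "Responses will not be linked to the study ID or other identifiable information". Section 16.2 repeats this: "Post-workshop survey results will be stored in Qualtrics and not linked to study ID, results will be entirely anonymous". In Appendix C the only grouping item is "What workshop did the participant attend", and its two answers are the two types of education, that is, the arm. The printed form has no field for workshop number, date, session, language, ethnicity or community health worker (CHW).

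**Paper record.** Under section 13.1.3.1, the four MCHH-PES items are copied into Qualtrics and also stay on paper at MCHH. The Appendix A form that carries them has an ID number, CHW, date and ethnicity.

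**Analysis.** Section 20.3.2 says "differences will be tested with Wilcoxon Rank-Sum tests for continuous or ordinal categorical data, Chi-Squared tests for unordered categorical data", with binomial tests for dichotomous data. It does not state the groups compared, the significance level or the number of sides, and it has no term for workshop.

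**The concern.** Women in one workshop share a session and a CHW, and sometimes a translator. The CHWs then read the survey aloud to them. Some positive correlation of answers within a workshop is therefore plausible. A test that counts each woman as an independent unit then understates the standard error of the arm difference.

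For most clustered data this can be put right at analysis. Here it cannot, because the field that any workshop-level, mixed-model or GEE analysis needs is not collected. Rewording section 20.3.2 alone would not help, and neither would correcting the primary analysis, because the survey is a separate, unlinked data set.

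The gap may also reach the primary outcome. Section 20.3.1 counts a stated wish to be screened later by a community provider towards uptake. In the printed forms, the questions on future screening and where it would take place are in UW-PSS Sections C and G. The REDCap fields listed in section 16.2 include no intention item. If that component is taken from the UW-PSS, it too could not be assigned to a workshop. MCHH-PES item 1 is only a partial substitute, because it does not ask where.

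**Working it through.** **1. The plan's own figures.** The document gives no error rate or power for the survey. Its only figures are the detectable rates in section 20.2 (125 per arm, one-sided 0.05). Exact one-sided Fisher power for independent women, at power 0.80/0.85/0.90, gives:

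| Control rate | Recomputed | Stated |
|---|---|---|
| 0.61 | 0.763 / 0.773 / 0.786 | 0.77 / 0.78 / 0.79 |
| 0.71 | 0.847 / 0.855 / 0.866 | 0.85 / 0.86 / 0.87 |
| 0.81 | 0.923 / 0.929 / 0.937 | 0.93 / 0.93 / 0.94 |

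Rounded up, all nine cells match. The plan's calculations therefore take women as independent throughout.

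**2. Which items are affected** (from the skip pattern in Appendix C).

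| Items | Answered by | Workshop recoverable? |
|---|---|---|
| Section A (four MCHH-PES items) | All women, both arms | Probably, from the MCHH paper form |
| Comfort; likelihood of repeat screening (Sections B, E, F) | Screened women, both arms | No |
| Future intention (Sections C, G) | Women not screened at the first offer, both arms | No |
| Preference for self-collection (B, C) | Control arm only | No between-arm test possible |
| Preference for a clinician, instructions, recommending the method (E) | Self-collectors only | No |

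**3. Error-rate formula.** Take workshops of 8 and let each woman answer an item with probability p, independently. The size-weighted mean number of respondents per workshop is E[n²]/E[n] = 1 + 7p. Then:

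- design effect DE = 1 + 7p × ICC
- true two-sided error = 2 × [1 − Φ(1.96/√DE)]

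The documents give no ICC, so 0.05, 0.10 and 0.20 are assumptions. For p, the section 20.2 range of 0.61 to 0.81 is used for illustration in both arms: p = 0.61 to 0.81 for items answered by screened women, and p = 0.19 to 0.39 for items answered by unscreened women.

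| Items | p | ICC 0 | 0.05 | 0.10 | 0.20 |
|---|---|---|---|---|---|
| Comfort, repeat | 0.61 | 5.0% | 7.5% | 10.1% | 15.0% |
| Comfort, repeat | 0.81 | 5.0% | 8.4% | 11.7% | 18.0% |
| Intention | 0.19 | 5.0% | 5.8% | 6.6% | 8.2% |
| Intention | 0.39 | 5.0% | 6.6% | 8.2% | 11.5% |
| Items answered by all 8 women | 1 | 5.0% | 9.2% | 13.3% | 20.6% |

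Worked example: p = 0.81, ICC = 0.10 gives DE = 1 + 7 × 0.81 × 0.10 = 1.567. Then 1.96/√1.567 = 1.566, and the two-sided error is 11.7%.

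**4. Check by simulation for items answered by all 8 women.** There were 15 workshops of 8 per arm, a five-level item and no arm effect. Two separate simulations of the Wilcoxon test gave 7.9%/12.8%/19.2% and 8.8%/12.1%/17.8% at ICC 0.05/0.10/0.20, close to the formula. In the second, a t-test on the 30 workshop means gave 4.5% to 5.4% across ICC 0 to 0.20. In the first, a linear model on workshop means with language gave 4.9% to 5.7%.

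**5. Language.** With language balanced across arms as in Table 1, a between-language variance of 0.10 and no other clustering, the Wilcoxon test rejected in 3.9% of trials. An unadjusted t-test on workshop means rejected in 2.0%, which is a reason to adjust workshop means for language. If workshops were randomised without regard to language, the Wilcoxon figure was 10.0%.

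**6. Re-identification.** With a workshop code, a woman who is the only decliner among 8 has a unique screening status. The probability is 8q(1 − q)⁷. For q = 0.19 this is 8 × 0.19 × 0.2288 = 0.35, and for q = 0.39 it is 8 × 0.39 × 0.0314 = 0.10.

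**The case against.** The strongest reply is that the plan does not clearly promise a between-arm test of these items. Section 20.3.2 names no groups, section 2 describes satisfaction as assessed qualitatively, and the preference items exist in one arm only. That stands, and it is why the point is conditional. Still, a rank-sum test needs independent groups, and the arm is the main grouping the form records. Anonymous answers also cannot be paired with intake data.

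Second, a reader might infer that the planned tests are bound to give too many false positives, at 8%, 13% and 19% for every item. The documents do not support this. The ICC is unknown: even for items answered by all 8 women, the rate is 5.8% at ICC 0.01 and 6.6% at 0.02. The higher figures apply only to such items, which are chiefly the four in Section A. Those can probably be traced to a workshop on paper.

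Third, a reader might infer that the missing language field inflates error by itself. With the balance in Table 1 it does not; the test becomes conservative. Nor do the secondary objectives name language groups. Only the primary objective does, and a breakdown by ethnicity is planned only for uptake.

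Fourth, anonymity is a deliberate protection, and a workshop code weakens it. It would be wrong to say that answers could then never be traced to a person: Appendix C records screening status, and REDCap holds study ID, workshop date and type of screening. This stands as a real cost of the fix.

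Fifth, the remaining items compare groups formed after randomisation (screened or unscreened women), and control women who self-collect later also enter Section E. A workshop code does not make those comparisons randomised. This also stands.

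Finally, this is a self-described pilot, the survey is secondary and no decision depends on it. That limits the weight of the point but leaves the missing field missing.

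**Conclusion.** The point holds in a limited form. As printed, the UW-PSS cannot be analysed by the randomised unit, and section 20.3.2 names only tests that ignore it. If comfort, repeat-screening or intention items are compared between arms and answers within workshops are positively correlated, the p-values will be too small and cannot be corrected later. With uptake of 0.61 to 0.81 and an ICC of 0.05 to 0.20, both assumed, the true error of a nominal 5% test runs from about 7.5% to 18% for comfort and repeat items and from about 6% to 12% for intention items. At ICC 0 there is none of this inflation. The same gap affects the intention part of the primary outcome only if that part is drawn from UW-PSS Sections C and G.

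The conclusion rests on the printed Appendix C, which section 13.1.3.2 presents as the full survey. The live Qualtrics form cannot be seen, and whether it keeps a usable time stamp is not stated.

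**What to change.** - **Survey form.** Add one staff-entered workshop code (1 to 30) to the start of the Qualtrics form, still unlinked to study ID. The workshop schedule then supplies the language. Reword sections 13.1.3.2 and 16.2 to say that responses carry a workshop code only, and withdraw the claim of complete anonymity. Keep the code apart from the REDCap screening data.
- **Section 20.3.2.** State the groups compared, the significance level and the number of sides. Compare arms on workshop-level means or proportions, for example by a permutation test that follows the actual allocation or a linear model on workshop means adjusted for language. Label comparisons among screened-only or unscreened-only women as descriptive.
- **Section 20.3.1.** Say which form supplies the wish for later screening.

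**Cost.** One field and a few sentences, less favourable p-values, and a small re-identification risk where one woman in a workshop has a unique screening status (a lone decliner in about 10% to 35% of workshops at the assumed uptake). If that risk is not acceptable, leave the form as it is and report the UW-PSS descriptively, without between-arm p-values.
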